9.6. Deviation from Analyses Planned in Protocol

The study was terminated early, therefore cohort 2 has only 2 participants and cohort 6 has none. Therefore the secondary objective, to compare safety and tolerability, PK, PD, and immunogenicity of ALXN1830 SC between Japanese and non-Japanese healthy participants cannot be met and the secondary endpoint the quantitative assessment of safety, PK parameters, PD parameters, and immunogenicity between Japanese and non-Japanese healthy participants cannot be analyzed.

10. Pharmacodynamics

Venous blood samples will be collected for measurement of IgA, IgM, IgG, and IgG subtypes (1 - 4), FcRn receptor occupancy, and CIC at timepoints described in the SoA (Protocol Section 1.3).

As data become available during the study, the timing of PD sampling may be altered in order to ensure appropriate monitoring of participants.

Whole blood for assessment of exploratory biomarkers will be collected as per the SoA (Protocol Section 1.3). Residual PK/PD samples may also be used for exploratory analyses.

10.1. Endpoints and Analysis

10.1.1. Endpoints

- Change in serum levels of IgA, IgM, IgG, and IgG subtypes (1 to 4)) over time
- FcRn saturation as measured by receptor occupancy
- Quantitative assessment of PD parameters between Japanese and non-Japanese healthy participants

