#### 2. INTRODUCTION

ALXN1830 is a humanized, affinity-matured IgG4 kappa mAb that binds to the FcRn and blocks FcRn-mediated recycling of IgG and IgG immune complexes (ICs), thereby lowering total IgG (including pathogenic autoantibodies) and ICs in circulation. As FcRn is also involved in albumin recycling, ALXN1830 was designed to specifically block the IgG-binding site but not the albumin-binding site on FcRn. Studies in both nonhuman primates and humans have demonstrated that ALXN1830 treatment leads to decreases in endogenous IgG levels without affecting serum albumin levels (Mezo, 2008; Nixon, 2015).

Immunoglobulin G can indirectly cause disease activity through the formation of ICs, which induce the production of inflammatory cytokines or promote antigen presentation and the pathogenic activity of T cells, which also provide help to B cells resulting in the production of additional pathogenic IgG antibodies (Blumberg and Lencer, 2005). The FcRn contributes to such immunopathology by both maintaining the levels of pathogenic IgG antibodies and orchestrating the inflammatory activities of IgG-ICs (Baker, 2009; Pyzik, 2015; Roopenian and Akilesh 2007).

There has been increasing recognition that FcRn blockade is a novel, reversible, and potentially effective means to treat a large number of autoimmune diseases in humans. The potential efficacy of FcRn blockade was originally supported by preclinical studies in experimental autoimmune myasthenia gravis (MG) in rats, wherein such FcRn blockade can impede both passive MG induced by administration of an anti-acetylcholine receptor antibody, or in active MG in rats that were immunized against the acetylcholine receptor (Liu, 2007). More recently, clinical studies in patients with MG and other IgG-mediated autoimmune diseases have demonstrated improvement in disease endpoints following treatment with anti-FcRn therapeutics.

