#### 4.3. Justification for Dose

Single and multiple IV doses of ALXN1830 have been administered in healthy participants, and in patients with WAIHA and PV. In healthy participants, single IV doses were given at 1, 3, 10 and 30 mg/kg (Study SYNT001-101), and multiple IV doses were given at 20 mg/kg qw for 3 doses and then q2w for 3 doses (Study SYNT001-104). In WAIHA (Study SYNT001-102) and PV (Study SYNT001-103) patients, IV doses of 10 mg/kg qw for 5 doses were given. Also, single SC doses of 750 mg and 1250 mg ALXN1830 have been administered in a limited number of healthy participants (Study ALXN1830-HV-105).

A physiologically based PK/PD model for IV dosing was established and was fitted to the IV PK/PD data from healthy participants. Due to the lack of robust SC data in humans, an SC PK/PD model is not yet available. However, the following has been observed:

- 1. The bioavailability (F) of ALXN1830 after SC administration is likely low:
  - a. Based on the preliminary results from the 5-week SC monkey toxicity study (Study 2455024), F after a single dose of 30 mg/kg SC in monkeys is around 21.5%.
- 2. The maximum reduction of IgG for ALXN1830 is likely similar between IV and SC at the same mg/kg dose:
  - a. At 100 mg/kg IV or SC in the 5-week Good Laboratory Practice (GLP) toxicology studies (Studies 2455-002 and 2455-024), the maximum IgG reduction was 68% after IV and 69% after SC.
  - b. At 750 mg SC or 10 mg/kg IV, similar IgG reduction was observed in a clinical study in healthy participants (Studies ALXN1830-HV-105, SYNT001-01).
- 3. ALXN1830 bioavailability after SC administration is 20%.

Based on these observations, ALXN1830 exposure, safety margin, and IgG reduction after SC administration was predicted (see Table 16). The following assumptions have been used:

ALXN1830 clearance (CL) and body weight have the following relationship:

 $CL = (Median CL) \times (body weight/median body weight)^{0.75}$ 

Table 16: Predicted ALXN1830 Exposure, Safety Margin, and Immunoglobulin G
Reduction after Subcutaneous Administration

Cohort	Dose (mg)	Body Weight (kg) a	Weekly Dose in mg/kg a,b	F	AUC of SC Dosing (h*µg/mL) a.c	Margin Based on NOAEL of Monkey Toxicology Studies a,d	Margin Based on 5-week Monkey SC Toxicology Study a,e	Margin Based on 27-week Monkey IV Toxicology Study a,f	Expected Maximum IgG Reduction (%) g
1	1500,	75	20	0.2	1451	5	4	24	-45

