c AUCSC = (Dose/CLIV) \* F, where CLIV is scaled as CLIV = (Median CLIV) × (body weight/median body weight)0.75. Median CLIV at 10 mg/kg = 239 mL/h with a median body weight of 82.7 kg (SYNT001-101); Median CLIV at 20mg/kg = 215 mL/h with a median body weight of 79 kg (SYNT001-104); Median CLIV at 30 mg/kg = 154 mL/h with a median body weight of 75.8 kg (SYNT001-101). Where median CLIV is not available at certain dose levels (eg 15 mg/kg), doses (mg/kg) are round up to obtain a conservative estimate. Median CLIV for 45 mg/kg is set to equal to median AUCIV at 30 mg/kg (2.03 mL/h/kg). The AUC represents AUC0-inf and AUCss for single and multiple doses respectively.

<sup>d Safety margin = (Monkey NOAEL in mg/kg) / (Human dose in mg/kg). Monkey NOAEL for weekly dosing is 100 mg/kg (Studies 2455-024 and 2455-016).

<sup>e Safety margin = (Monkey AUC0-120h at NOAEL) / (Predicted human AUCSC). Day 29 AUC0-120h =  $6420 \text{ h*}\mu\text{g/mL}$  at 100 mg/kg weekly SC (Study 2455-024).

f Safety margin = (Monkey AUC0-Tlast at NOAEL) / (Predicted human AUCSC). Day 92 AUC0-Tlast = 34800 h\*μg/mL at 100 mg/kg weekly IV (Study 2455-016).

<sup>g IgG reduction is based on predicted IgG reduction at equivalent IV dose in mg/kg. IgG reduction at median body weight is presented.

participant) or 24-fold (for a 75-kg participant) based on the NOAEL exposure from the 27-week IV monkey toxicity study. More importantly, a 30 mg/kg IV single dose has been tested in healthy participants and this starting dose of 1500 mg SC is expected to be roughly one-fifth to one-eighth of the exposure at 30 mg/kg IV, based on the low bioavailability observed in monkeys for ALXN1830 and in healthy participants from other anti-FcRn compounds. Based on these observations, the expected maximum IgG reduction at 1500 mg SC would be around -45% from baseline.

In the SAD portion, the SC dose will be escalated 1.5-fold from 1500 mg (Cohort 1) to 2250 mg (Cohort 2). An SRC review of safety, tolerability, and IgG data will be conducted before each dose escalation. Staggered dosing and pre-specified stopping rules based on safety and IgG reduction will be implemented in all cohorts.

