# 8.6. Pharmacodynamics

Venous blood samples will be collected for measurement of IgA, IgM, IgG, and IgG subtypes (1 - 4), FcRn receptor occupancy, and CIC at timepoints described in the SoA (Section 1.3). Blood will be separated into 2 aliquots for Igs; 1 each for Ig and subclass testing. A separate sample will be collected for CIC, and a separate sample will be collected for FcRn receptor occupancy on human monocytes. The actual date and time (24-hour clock time) of each sample will be recorded.

As data become available during the study, the timing of PD sampling may be altered in order to ensure appropriate monitoring of participants. Detailed instructions on the procedure for collecting, processing, storing, and shipping serum samples for PD analysis will be provided in the laboratory manual.

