10.1.2. Analysis of the Endpoints

Pharmacodynamic analyses will be performed using the PD Set.

The endpoint regarding the quantitative assessment of PD parameters between Japanese and non-Japanese healthy participants cannot be analyzed due to early termination of the study.

Missing concentration data for all participants who are administered scheduled study treatments will be considered as non-informative missing and will not be imputed. No concentration estimates will be provided for missing sample values.

For the PD/biomarker levels, actual values, changes from baseline and percentage change from baseline will be summarized by time point for each treatment using the following descriptive statistics: number of participants, arithmetic mean, SD, CV, geometric mean, geometric CV, median, minimum, and maximum.

Mean PD/biomarker levels (change from baseline and percentage change from baseline) versus scheduled time profiles will be presented in figures.

Individual PD/biomarker levels (change from baseline and percentage change from baseline) versus scheduled time profiles will be presented similarly.

PD/biomarker levels, change from baseline and percentage change from baseline will be presented in a data listing by participant.

11. Immunogenicity

The population used for immunogencity analyses will be the Immunogenicity Set (IGS).

Samples for immunogenicity should be collected at times specified in the SoA (Protocol Section 1.3).

The immunogenicity analyses will include an analysis of anti-drug antibodies (ADA) using descriptive statistics.

The actual date and time (24-hour clock time) of each sample will be recorded.

All samples that are positive in a screening assay will be confirmed for antibody specificity and further characterized for titer. All samples that are confirmed positive for ADA will be evaluated for the presence of neutralizing antibodies.

Participants found to have anti-ALXN1830 antibodies still present at the end of the study will be requested to return to the clinic for up to 1 year (from the first drug administration) or until ADA titers return to baseline levels (whichever occurs first). The follow-up visits are to be scheduled at 90-day intervals for blood collection to assess ADA.

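### IgG4 is summarised as measured although ALXN1830 is itself an IgG4: if the subclass assay detects the drug, the IgG4 fall is understated, and more so at higher doses

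*SAP*

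**What the plan says.** The protocol's Introduction states that "ALXN1830 is a humanized, affinity-matured IgG4 kappa mAb that binds to the FcRn". The SAP makes the subclasses an endpoint in section 10.1.1: "Change in serum levels of IgA, IgM, IgG, and IgG subtypes (1 to 4)) over time". For every PD marker, section 10.1.2 plans that "actual values, changes from baseline and percentage change from baseline will be summarized by time point for each treatment". No step adjusts for drug in the sample, and no caution is attached to IgG4.

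On the assay itself, protocol section 8.6 says only that "Blood will be separated into 2 aliquots for Igs; 1 each for Ig and subclass testing", and leaves sample handling to a laboratory manual. The type of subclass method and its specificity against ALXN1830 are not described.

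In the protocol's Schedule of Activities, IgG subtypes and PK are drawn at the same time points in every cohort, so each post-dose IgG4 value should have a concurrent drug concentration.

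**The concern.** Of the four subclasses, IgG4 is the one that shares the drug's isotype. An assay that recognises IgG4 might count ALXN1830 as well as the participant's own IgG4. Baseline is free of drug, because prior exposure to ALXN1830 is an exclusion criterion, but post-dose samples are not. Any drug that is counted would make the IgG4 fall look smaller than it is.

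The error would not be constant. It would rise with drug concentration, and therefore with dose, and it would be largest in participants who start with little IgG4. SAP section 7.1 puts Cohorts 3, 4 and 5 in adjacent columns, so a reader could take a weaker IgG4 response at the higher dose as pharmacology. SAP section 11.1.2 also plans PD response by immunogenicity response. If antidrug antibodies change drug levels, the masking could differ by ADA status too.

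**Working it through.** **Inputs from the documents (protocol section 4.3, Table 16 and footnote c).** Bioavailability F = 0.20. Median IV clearance is 239 mL/h at 82.7 kg (10 mg/kg), 215 mL/h at 79 kg (20 mg/kg) and 154 mL/h at 75.8 kg (30 mg/kg). For multiple dosing the AUC is the steady-state value. The dosing interval is 1 week = 168 h (SAP section 9.2).

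**Step 1: reproduce Table 16 at 75 kg.** AUC = F × dose / [CL × (75 / median weight)^0.75].

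- 750 mg: 0.2 × 750,000 µg / [239 × (75/82.7)^0.75] = 675.3, against 675 h·µg/mL stated.
- 1500 mg: 0.2 × 1,500,000 / [215 × (75/79)^0.75] = 1450.8, against 1451.
- 2250 mg: 0.2 × 2,250,000 / [154 × (75/75.8)^0.75] = 2945.4, against 2948.

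All three agree within 0.1%.

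**Step 2: average drug concentration on weekly dosing.** Average = AUC / 168 h, and 10 µg/mL = 1 mg/dL.

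- 750 mg: 675/168 = 4.02 µg/mL = 0.40 mg/dL.
- 1500 mg: 1451/168 = 8.64 µg/mL = 0.86 mg/dL.
- 2250 mg: 2948/168 = 17.5 µg/mL = 1.75 mg/dL.

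A 3-fold dose range gives a 2948/675 = 4.4-fold range in drug.

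**Step 3: masking if the assay reads drug one for one.** With baseline B, drug concentration C and true fractional fall r, measured IgG4 is (1 − r)B + C. The apparent fall is therefore r − C/B, and the masking in percentage points is 100 × C/B, whatever r is. Baseline IgG4 is not in the documents, so a range is assumed.

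| Assumed baseline IgG4 (mg/dL) | 750 mg qw | 1500 mg qw | 2250 mg qw |
|---|---|---|---|
| 5 | 8.0 | 17.3 | 35.1 |
| 10 | 4.0 | 8.6 | 17.5 |
| 20 | 2.0 | 4.3 | 8.8 |
| 40 | 1.0 | 2.2 | 4.4 |
| 80 | 0.5 | 1.1 | 2.2 |

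As an illustration, take the same true fall of 70% at both ends of the dose range and a baseline of 10 mg/dL. The apparent fall would be 70 − 4.0 = 66% at 750 mg and 70 − 17.5 = 52.5% at 2250 mg, which looks like an inverse dose response.

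**Step 4: away from the weekly average.** Masking is proportional to C. If the level near peak is 2 to 4 times the average (an assumption), masking at 2250 mg with a baseline of 40 mg/dL is 8.8 to 17.5 points. It is smaller at trough. Between its full profiles, Cohort 3 is sampled predose only on Days 8, 15, 29, 36, 43, 50, 57, 64 and 71. Cohorts 4 and 5 are sampled predose only on Days 8 and 15. Late follow-up samples should contain little or no drug.

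**Step 5: total IgG.** Inclusion requires at least 1,000 mg/dL. At 2250 mg the average drug level adds at most 100 × 1.75/1,000 = 0.18 points, and about 0.7 points at four times the average. Against the 300 mg/dL threshold, 1.75/300 = 0.6%.

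**The case against.** The strongest objection is that the premise is not in the documents. They do not call the subclass method an immunoassay, and they say nothing of its specificity. That usually belongs in assay validation, and the laboratory manual is not available here. A reader might infer that the assay will read the drug and that the planned IgG4 results are therefore biased. The documents do not support that; they support only that it could happen and that the plan does not say. This part of the objection stands.

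The size also depends on an undocumented baseline. The 35-point figure belongs to the lowest assumed baseline at the highest dose. At 40 mg/dL or more, masking at the weekly average is at most 4.4 points, and many samples are taken at trough. This stands too.

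The reach is narrow. The listed secondary PD endpoint is total serum IgG and FcRn occupancy. IgG4 enters descriptive summaries only; the power model in SAP section 9.5 is for PK parameters. The dose-escalation and immunoglobulin stopping rules use IgG, IgA and IgM, not IgG4. Individual PK and PD listings would let a careful reader set IgG4 against drug level.

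Finally, subtracting drug by default could produce the opposite error. Suppose the assay does not see the drug, the baseline is 5 mg/dL and the true fall is 70%. At 2250 mg the net value is 1.5 − 1.75 = −0.25 mg/dL, an apparent 105% fall. At a baseline of 10 mg/dL it is 3 − 1.75 = 1.25, an apparent 87.5% fall. Values at or below zero also defeat the geometric mean and CV that section 10.1.2 requires. So the net value should not replace the measured one, and the fix is built accordingly.

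None of this removes the gap. The raw IgG4 summaries cannot be read as endogenous IgG4 until assay specificity is stated.

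**Conclusion.** The point holds in conditional form, as a low-cost improvement and not as a flaw in the main analysis. If the subclass assay detects ALXN1830, measured IgG4 understates the fall by 100 × C/B points. At the weekly average that is 35 to 2 points at 2250 mg and 8 to 0.5 points at 750 mg, for baselines from 5 to 80 mg/dL.

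This rests on four assumptions: one-for-one detection, the Table 16 predicted exposures at 75 kg, the assumed baselines, and the weekly average standing in for the level at sampling.

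Two stronger conclusions are tempting. One is that any IgG4 dose pattern in this study is an artefact. That would need evidence of cross-reactivity and of low baselines, and the documents give neither. The other is that the study's PD conclusions are compromised. They are not: the effect on total IgG is a fraction of a point at average levels, and FcRn occupancy is a separate measurement.

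**What to change.** In SAP section 10.1.2:

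1. Keep measured IgG4 as the reported value, and have the laboratory confirm whether the subclass assay detects ALXN1830 and, if so, with what recovery.
2. If it does not, state that and use the measured value alone.
3. If it does, or this is unknown, add a sensitivity summary of net IgG4: measured IgG4 minus concurrent serum ALXN1830, converted to the same units and scaled by the confirmed recovery where known. Where net values are zero or negative, give arithmetic summaries only.
4. In that case, base IgG4 dose comparisons on samples with ALXN1830 below quantification, or on agreement between the measured and net summaries. Drug-free samples may come late, so they may describe recovery better than the nadir.

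The cost is one query to the laboratory, one derived variable and one extra table, all from samples already scheduled. The limitation is that the net value rests on one-for-one detection until recovery is confirmed, and should be labelled so.

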10.1.2. Analysis of the Endpoints

Pharmacodynamic analyses will be performed using the PD Set.

The endpoint regarding the quantitative assessment of PD parameters between Japanese and non-Japanese healthy participants cannot be analyzed due to early termination of the study.

Missing concentration data for all participants who are administered scheduled study treatments will be considered as non-informative missing and will not be imputed. No concentration estimates will be provided for missing sample values.

For the PD/biomarker levels, actual values, changes from baseline and percentage change from baseline will be summarized by time point for each treatment using the following descriptive statistics: number of participants, arithmetic mean, SD, CV, geometric mean, geometric CV, median, minimum, and maximum.

Mean PD/biomarker levels (change from baseline and percentage change from baseline) versus scheduled time profiles will be presented in figures.

Individual PD/biomarker levels (change from baseline and percentage change from baseline) versus scheduled time profiles will be presented similarly.

PD/biomarker levels, change from baseline and percentage change from baseline will be presented in a data listing by participant.

11. Immunogenicity

The population used for immunogencity analyses will be the Immunogenicity Set (IGS).

Samples for immunogenicity should be collected at times specified in the SoA (Protocol Section 1.3).

The immunogenicity analyses will include an analysis of anti-drug antibodies (ADA) using descriptive statistics.

The actual date and time (24-hour clock time) of each sample will be recorded.

All samples that are positive in a screening assay will be confirmed for antibody specificity and further characterized for titer. All samples that are confirmed positive for ADA will be evaluated for the presence of neutralizing antibodies.

Participants found to have anti-ALXN1830 antibodies still present at the end of the study will be requested to return to the clinic for up to 1 year (from the first drug administration) or until ADA titers return to baseline levels (whichever occurs first). The follow-up visits are to be scheduled at 90-day intervals for blood collection to assess ADA.

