## 2.2. Background

A detailed description of the chemistry, pharmacology, efficacy, safety, and toxicology data available for ALXN1830 is provided in the Investigator's Brochure (IB).

Nonclinical studies have assessed both the potential toxicity and primary PD effects associated with ALXN1830 antagonism of IgG binding to FcRn and IgG recycling mediated by FcRn. The administration of ALXN1830 to cynomolgus monkeys by qw IV infusion at doses from 5 to 100 mg/kg for 2 to 27 weeks was well tolerated, with the exception of immunogenicity related effects of this humanized mAb in monkeys, and produced dose-dependent, specific, and reversible reductions in circulating IgG levels. No effects on IgA, IgM, or albumin levels were observed.

ALXN1830 has been evaluated in 4 completed clinical studies: SYNT001-101 (healthy participants, single dose study), SYNT001-102 (WAIHA patients, 5 × 10 mg/kg qw), SYNT001-103 (PV patients, 5 × 10 mg/kg qw), and SYNT001-104 (healthy participants, 3 × 20 mg/kg qw, then 3 × 20 mg/kg q2w), and 1 clinical study ALXN1830-HV-105, in healthy participants, was paused² after completing the first cohort and part of the second cohort (single SC doses of 750 mg and 1,250 mg). In all the clinical studies, ALXN1830 was shown to increase the catabolism of IgG, as manifested by decreased total IgG in serum in a dose-dependent manner up to 64% decrease from baseline, with no effects on IgA, IgM, or albumin. ALXN1830 also decreased the level of circulating IgG IC. This predicts that ALXN1830 will also accelerate degradation of endogenous circulating IgG autoantibodies and IgG IC specifically involved in the pathogenesis of autoimmunity.

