As shown in Table 16 the first MAD cohort will be administered 750 mg SC qw for 12 weeks (Cohort 3). On a mg/kg basis, the 750 mg SC qw dose represents at least a 7 to 35-fold safety margin when compared to the NOAEL exposures of the 5-week SC and 27-week IV monkey GLP studies. The first MAD cohort (750 mg, qw, Cohort 3) may start at the same time as the single-dose Cohort 1 (1500 mg) while the rest of the MAD cohorts will start after SRC review of the previous MAD cohorts. While all the MAD cohorts have a treatment duration of 4 weeks, Cohort 3 (750 mg SC qw for 12 weeks) is of an extended duration to enable the evaluation of immunogenicity and safety after long term administration of ALXN1830.

The SC multiple doses will be escalated 2-fold from 750 mg qw to 1500 mg qw (Cohort 4), and then 1.5-fold to 2250 mg qw (Cohort 5) after SRC review. At these dose levels, the expected maximum IgG reduction after 4 qw doses is expected to be around 69% and 72%, respectively, which is similar to that observed with 20 mg/kg IV in Study SYNT001-104 (after the 3 qw loading doses).

As shown in Table 15, Cohort 6 will assess the safety, tolerability, PK, PD, safety, and immunogenicity of ALXN1830 in Japanese participants at the highest tolerable dose established in the non-Japanese participants (ie, either up to 1500 mg or up to 2250 mg SC qw for 4 doses). The exact dose and time of dosing will be determined after SRC review of all safety data through Day 36 from Cohort 5 as well as from all prior cohorts. Japanese participants are expected to have a lower mean body weight than non-Japanese participants. This and other differences (eg, genetics) may impact PK/PD in Japanese participants. Although Japanese participants may potentially have slightly higher exposure based on the lower mean body weight, the overall exposure in Japanese participants is predicted not to exceed established safety margins.

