## **Type of Participant**

- 2. Participants who are healthy as determined by medical evaluation including medical history, physical examination, laboratory tests, and cardiac monitoring.
- 3. Participant agrees to not donate blood for 4 months after completion of their last study visit.
- 4. Baseline IgG concentrations ≥ 1,000 mg/dL at Screening.
- 5. Baseline IgA and IgM above the lower limit of normal at Screening.
- 6. Participants must have had vaccination against pneumococcus (Pneumovax 23 [PPSV23]) at least 28 days, and maximally 4 years prior to Day 1.
- 7. Participants must have had seasonal influenza vaccination for the current season at least 28 days prior to Day 1.
- 8. Participants of Japanese descent (Cohort 6) are defined as:
  - a. First generation (born to 2 Japanese parents and 4 Japanese grandparents).
  - b. Participant must have been born in Japan, and not have lived outside Japan for greater than 10 years.
  - c. Lifestyle, including diet, must not have significantly changed since leaving Japan.

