7.2. Key Definitions

End of Study (EOS)

The EOS for each participant is defined as the date the last participant completes the last visit as shown in the Schedule of Activities in Section 1.3 of the Protocol.

Trial day

If the event date \geq date of first dose of IP, trial day = event date – date of first dose of IP + 1. If the event date < date of first dose of IP, trial day = event date – date of first dose of IP.

Nominal Time

Nominal time is the scheduled measurement time relative to time 0. Time 0 is the time of start of study drug dosing on Day 1.

Baseline Value

Baseline value will be defined as the last non-missing value recorded prior to first intake of study treatment.

Change from Baseline (CFB)

Sponsor: Alexion Pharmaceuticals, Inc.; Protocol No.: ALXN1830-HV-108

CFB = Post-baseline value - Value at baseline

7.3. **Missing Data**

For participants who are withdrawn from the study prior to the end of the study, all data collected up to the point of discontinuation will be used for analysis. There will be no imputation for missing data, unless otherwise specified.

7.4. **Visit Windows**

If there are multiple planned assessments for any study procedure at a given time point the latest nonmissing value will be used for summarization. Unscheduled assessments will be listed and will be used to flag baseline visit if this is the last non-missing assessment before the first dose of study drug, but unscheduled assessments will not be included in the summarization.

Pooling of Centers 7.5.

Not Applicable.

7.6. **Subgroups**

Not Applicable.

8. Participant Disposition, Demographic, Other Baseline Characteristics and Medication

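### The SAP asks for the geometric mean and geometric CV of change and percent change in immunoglobulins, which are undefined wherever IgG has fallen

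*SAP*

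**What the plan says.** SAP 10.1.2 covers three forms of each pharmacodynamic or biomarker level at once: "actual values, changes from baseline and percentage change from baseline will be summarized by time point for each treatment using the following descriptive statistics". The list is "number of participants, arithmetic mean, SD, CV, geometric mean, geometric CV, median, minimum, and maximum". Nothing limits the geometric statistics to actual values.

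SAP 7.2 fixes the sign of the change: "CFB = Post-baseline value - Value at baseline". A fall is therefore negative. The first endpoint in SAP 10.1.1 is "Change in serum levels of IgA, IgM, IgG, and IgG subtypes (1 to 4)) over time", and change in serum IgG is a secondary endpoint of the trial (SAP 5.2). Protocol 9.4 names percent change in IgG as the pharmacodynamic parameter.

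The protocol expects large falls. For the 1500 mg single dose, "the expected maximum IgG reduction at 1500 mg SC would be around -45% from baseline". For 1500 mg and 2250 mg weekly, "the expected maximum IgG reduction after 4 qw doses is expected to be around 69% and 72%, respectively". Table 16 of the protocol adds 48% for the 2250 mg single dose and 68% for 750 mg weekly. Earlier studies of the drug "decreased total IgG in serum in a dose-dependent manner up to 64% decrease from baseline".

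The general list of statistics in SAP 7.1 contains no CV and no geometric statistics. The list in SAP 10.1.2 is the same as the one for serum drug concentrations in SAP 9.3.3.

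**The concern.** A geometric mean and a geometric CV are computed on logarithms, so they suit quantities that are always positive, such as concentrations. A list that works for drug concentrations has been applied to differences, which are expected to be negative on active drug and close to zero on placebo.

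The SAP does not define a ratio to baseline or say what to do with zero or negative values. The request therefore cannot be carried out as written for two of the three quantities it covers, one of which is the parameter the protocol names for IgG. What appears in the table is left to the programmer. It may be a blank or a not-calculable flag, which is harmless. It may instead be a number computed from whichever values happen to be positive, which would mislead because it has a reduced and unstated n and can have the wrong sign.

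**Working it through.** The plan states no figure to reproduce here. The check applies the definitions to the protocol's expected IgG changes.

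**Formulas.** The SAP gives none, so the standard ones are used.
- Geometric mean = exp(mean of ln x).
- Geometric CV = sqrt(exp(variance of ln x) − 1).
- Both need every x > 0.
- Percent change = 100 × (post − baseline) / baseline.

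**Step 1: expected maximum change on active drug.** Baseline is set at 1,000 mg/dL, the entry minimum ("Baseline IgG concentrations ≥ 1,000 mg/dL at Screening", Protocol 5.1). Expected reductions are from Protocol 4.3 and Table 16.

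| Cohort | Expected % change | Post (mg/dL) | Change (mg/dL) | ln(change) | Post/baseline |
|---|---|---|---|---|---|
| 1 | −45 | 550 | −450 | undefined | 0.55 |
| 2 | −48 | 520 | −480 | undefined | 0.52 |
| 3 | −68 | 320 | −680 | undefined | 0.32 |
| 4 | −69 | 310 | −690 | undefined | 0.31 |
| 5 | −72 | 280 | −720 | undefined | 0.28 |

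The logarithm of percent change is undefined in the same way. The ratio in the last column is always positive.

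**Step 2: could between-participant spread rescue it at nadir?** The documents give no SD for individual percent change, so 5 to 15 points is assumed, with a normal model and 6 active participants per cohort. P(all six ≤ 0) = Φ(−mean/SD)^6.
- Mean −45, SD 10: Φ(4.5)^6 = 0.99998.
- Mean −45, SD 15: Φ(3)^6 = 0.992.
- Means −68 and −72, any SD from 5 to 15: above 0.9999.

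At nadir there is in effect no usable value.

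**Step 3: partial recovery on active drug.** Assume mean −10 and SD 10. P(change > 0) = 1 − Φ(1) = 0.159, so 6 × 0.159 = 0.95 participants are expected to have a usable logarithm. Across many simulated values, the geometric mean of the positive ones is about +3.2%, against a true mean of −10%. As an invented example, changes of −18, −12, −9, −6, −3 and +2% have an arithmetic mean of −46/6 = −7.7%. The positives-only geometric mean is +2.0%, from one person.

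**Step 4: placebo, true change 0.** SAP 4.1 says Cohort 2 has only 2 participants and Cohort 6 has none. If Cohorts 1, 3, 4 and 5 are full, placebo n is 4 × 2 = 8, plus at most 2 from Cohort 2, so 8 to 10.
- P(at least one value ≤ 0) = 1 − 0.5^8 = 0.996 for n = 8 and 1 − 0.5^10 = 0.999 for n = 10.
- Visit schedules differ between cohorts. At time points that only one cohort attends, n is 2 and the probability is 1 − 0.5^2 = 0.75.
- Simulated average of a positives-only geometric mean (SDs assumed):

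| n | SD 8 | SD 10 |
|---|---|---|
| 8 | +4.9% | +6.2% |
| 10 | +4.8% | +6.0% |

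At n = 8 the 5th to 95th percentile range is about 1.4 to 10 for SD 8 and 1.8 to 12 for SD 10. The direction is certain, because only positive values enter. The size is not.

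**Step 5: does the ratio behave?** For six invented changes of −72, −70, −69, −68, −67 and −66%, the ratios are 0.28, 0.30, 0.31, 0.32, 0.33 and 0.34.
- Their geometric mean is 0.3127, and 100 × (0.3127 − 1) = −68.7%.
- The geometric CV is 7.0%.
- The arithmetic mean of the changes is −68.7% and their SD is 2.16.
- The arithmetic CV of the changes is 100 × 2.16 / (−68.7) = −3.1%, a negative CV.

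The ratio gives a sensible result. The CV of change does not, and it becomes unstable as the mean approaches zero.

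**The case against.** The strongest reply is that little is lost. The same sentence of SAP 10.1.2 also requests n, arithmetic mean, SD, median, minimum and maximum, all of which are valid for negative values. The section adds mean and individual profiles of change and percent change, and listings by participant. No hypothesis is tested (Protocol 9.1), so no inference rests on the geometric statistics. This stands, and it limits the point to part of a descriptive table.

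A reader might infer that the table will show a false rise in IgG. The documents do not support that as a prediction. It needs a program that drops non-positive values without comment and prints the remainder. The SAP names SAS but gives no procedure or dropping rule, and a not-calculable entry is equally possible. What the text itself supports is that the statistics are undefined.

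A reader might also infer that percent change in FcRn occupancy is undefined because the pre-dose value is near zero. The documents refer only to receptor occupancy on human monocytes and give no unit, assay readout or pre-dose value. A free-receptor or signal readout could have a non-zero baseline. This is a question for the sponsor and has not been shown to be an error.

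The phrase about appropriateness in SAP 7.1 does not rescue the list. It concerns summarising by treatment and period, not which statistics suit which quantity.

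**Conclusion.** The point holds as an error of specification. For change and percent change from baseline, SAP 10.1.2 requests two statistics that do not exist on active drug while IgG is suppressed. This follows from the SAP's definition of change and the protocol's expected falls of about 45% to 72%, whatever plausible SD is taken. On pooled placebo they are undefined with probability of about 0.996 or more when 8 to 10 participants contribute, on the assumption that changes are symmetric around zero. Geometric statistics remain sound for positive actual values.

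The endpoint itself survives through the arithmetic mean, SD, median, minimum and maximum. The misleading figure (roughly +5% to +6% on placebo, or a positive value during partial recovery on active drug) is conditional on silent dropping of non-positive values and on assumed SDs of 8 to 10 points. It should be read as an illustration of the risk. The correction should be made, but it is modest.

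**What to change.** In SAP 10.1.2, split the list of statistics by quantity:

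- **Actual values (positive) and the ratio to baseline (post/baseline):** allow geometric mean and geometric CV, with the geometric mean ratio back-transformed as 100 × (ratio − 1) and shown as a percent change.
- **Change and percent change:** n, arithmetic mean, SD, median, minimum and maximum. Drop geometric mean, geometric CV and arithmetic CV. The last is negative when the mean change is negative and unstable when it is near zero.
- **FcRn:** state the reporting scale. Only if it is percent occupancy with a pre-dose value at or near zero, replace percent change with absolute change in percentage points.

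The cost is SAP wording and table shells, with no new data. If the tables already exist, check how the affected cells were produced.
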